Pilot Implementation of Depression Screening and Treatment for Adolescents in Mozambican Primary Care

NCT05476237

July 30, 2025

BACKGROUND

Study Purpose and Rationale

Mental disorders are the number one cause of disability in adolescents worldwide, accounting for 45% of years lived with disability (Gore, Bloem et al. 2011). It is estimated that 90% of adolescents live in lower middle-income countries (LMICs), (Organization 2008) and that 10-20% of these adolescents have one or more mental disorders (Erskine, Moffitt et al. 2015). Despite the substantial burden of mental illness in LMICs, adolescent mental health services are extremely limited in these regions.(Morris, Belfer et al. 2011) Because untreated mental illness hinders individual, social, and economic prosperity in the long term, (Chen, Cohen et al. 2006, Erskine, Moffitt et al. 2015) improving adolescent mental health services has become a focus of global development efforts (Collins, Insel et al. 2013, Votruba, Thornicroft et al. 2016). In high-income countries, mental healthcare integrated into primary care settings is effective for treating adolescent mental illness (Asarnow, Rozenman et al. 2015). Mental health services delivered by non-specialists (task-shifting) within primary care of LMICs has been proposed as an efficient and sustainable way to close the adolescent mental health treatment gap (Patel, Kieling et al. 2013, Juengsiragulwit 2015). However, research is needed to determine how to effectively integrate interventions for managing adolescent mental disorders within LMIC primary care settings (Patel, Kieling et al. 2013, Juengsiragulwit 2015).

Mozambique is the fourth poorest country in the world (The World Bank. World Bank Open Data. Washington) and has just 15 psychiatrists and 180 psychologists to serve its population of 29 million (Santos, Wainberg et al. 2016). Given this scarcity of human resources, the Mozambican Ministry of Health (MoH) has focused on integrating psychiatric treatment into primary care, utilizing a task-shifting approach. In 1996, the MoH began training PsyTechs to deliver psychiatric services at primary care clinics through a 30-month theoretical and practical course, and PsyTechs now practice in all 135 districts of Mozambique (Santos, Wainberg et al. 2016). However, even with the introduction of PsyTechs, there are still just 1.48 mental health specialists for every 100,000 Mozambicans (Santos, Wainberg et al. 2016). Since 2017, the MoH has begun further expanding access to adult mental health services by training nonspecialists (nurses, medical technicians, and community health workers) to screen for mental disorders and provide treatment for common mental illnesses or referrals to specialized care for serious mental

illnesses. Despite this progress toward increasing services for adults, Mozambique continues to have very little infrastructure for treatment of adolescent mental disorders. The results of this study will contribute an understanding of how to integrate mental health treatment for children and adolescents in primary care clinics of low-resource settings, and its impact on patient outcomes. It will also produce data on the challenges and facilitators to implementation of mental healthcare for adolescents in these settings. This knowledge will be applied to scale-up of services in Mozambique and may be used to inform scale-up of interventions for youth globally, helping to reduce the global mental health treatment gap.

Research Aims & Abstracts

We aim to examine patient and implementation outcomes of task-shifted depression screening and group IPT-A compared to treatment as usual in a pilot cluster-randomized trial at four PCCs. Guided by Proctor's Taxonomy of Implementation Outcomes (Proctor, Silmere et al. 2011), we will assess patient and implementation outcomes through quantitative measures and post-treatment qualitative interviews with adolescents and providers in the IPT-A and TAU study arms. We hypothesize that the IPT-A arm will have better patient and implementation and patient outcomes than TAU.

Globally, mental disorders are the largest contributor to burden of disease in adolescents (Gore Bloem et al. 2011). However, the majority of adolescents with mental illness in low- and middle-income countries (LMICs) do not have access to treatment (Kieling, Baker-Henningham et al. 2011, Patel, Kieling et al. 2013) and contextually appropriate strategies for delivering evidence-based practices for managing mental disorders are needed to expand services to these areas. To broaden engagement in care, new settings for adolescent mental health services must be identified. Evidence-based interventions for managing adolescent mental disorders integrated within primary care have been effective in high-income countries (Asarnow, Rozenman et al. 2015) but very limited data exist on how to adapt and implement these EBP in LMIC primary care (Patel, Kieling et al. 2013, Mertens, Ward et al. 2014). We previously conducted a qualitative assessment of barriers and facilitators to implementation from the perspective of adolescents, caregivers, providers, and policymakers. We then developed our plan to implement integrated adolescent depression services by holding a series of workshops with local stakeholders—including Ministry of Health and Education staff involved in adolescent, mental health, and

primary care programming; staff from local NGOs that have experience implementing adolescent health programs in primary care; and primary care providers. Now we aim to pilot test the implementation strategy developed in these workshops. We will examine patient and implementation outcomes of depression screening and group IPT-A compared to treatment as usual in a pilot cluster-randomized trial at four primary PCCs with two PCC as the IPT-A arm and two PCC as the TAU arm.

STUDY DESIGN

We will examine patient and implementation outcomes of depression screening and group interpersonal therapy for adolescents (IPT-A) compared to treatment as usual in a pilot cluster randomized trial at four primary care clinics (PCC). Two PCC will be randomized to routine screening and IPT-A (intervention) and the other two PCC will be randomized to treatment as usual (TAU). In the IPT-A arm, providers (nurses and/or medical technicians) at PCCs will be trained to conduct paper-based depression screening as part of routine clinical care. Two providers (nurses and/or medical technicians) per clinic will be trained to facilitate group IPT-A. In the TAU arm, primary care providers will continue referring adolescents to specialized mental health services per existing protocol (when they believe the adolescent is struggling with a mental health problem or when the adolescent/their caregiver requests a referral to mental health services). Treatment providers in the TAU arm are the Psychiatric Technicians and psychologists at primary care clinics to whom adolescents are currently referred.

Study procedures

In the treatment study arm, we are evaluating the impact of IPT-A on depression symptoms in adolescents as well as the feasibility and acceptability of its introduction in primary care clinics. Therefore, adolescents identified as having depression, via screening on the PHQ-A, will be referred to IPT-A treatment groups instead of being referred to Psychiatric Technicians and psychologists in Mental Health Services at the PCC who provide unstructured psychotherapy (TAU).

IPT-A (Treatment) Study Arm: Prior to initiation of the pilot study, we will train providers at the PCC in the IPT-A arm to screen for depression using the Patient Health Questionnaire for

Adolescents (PHQ-A). Training will include didactics and role-plays to practice administration of the PHQ-A with corrective feedback and evaluations. Two providers per PCC will be selected to be trained on delivery of group IPT-A. Training will occur via an apprenticeship model which includes trainers (i.e., non-local experts in the mental health intervention), supervisors (i.e., local individuals chosen for an advanced role), and counselors (i.e., local individuals who provide the interventions). A group IPT-A training expert will train two psychologists from the MoH. Following this, the MoH psychologists will train the two staff members at the IPT-A arm PCC to facilitate group IPT-A. The MoH psychologists will supervise PCC providers for an additional 3 months to achieve competency prior to pilot trial initiation.

Every adolescent who attends PCCs will be screened for depression as part of their routine clinical care. Providers will use the PHQ-A for screening. Using a script, trained research assistants will introduce the study to adolescents who screen positive for depression and their caregivers. If interested, research assistants will collect patient demographic data (age in years, gender) on a questionnaire to verify eligibility.

Group IPT-A begins with one individual session, followed by ten group sessions, and ends with one individual session. As part of each Group IPT-A session, providers will collect data from adolescents on depression symptoms using the PHQ-A at treatment initiation, 6 weeks after treatment initiation (treatment midpoint), 12 weeks after treatment initiation (end of treatment), and 24 weeks after treatment initiation (3-month follow-up). The Project Coordinator will call adolescents who do not enter or who discontinue treatment to arrange data collection at these time points. For adolescents who do not enter treatment, the first scheduled session will be considered the “treatment initiation” timepoint.

Data on treatment fidelity will be collected via the Group IPT-A Fidelity Checklist, completed by the local IPT-A trainers at 10 randomly-selected sessions for each provider. On the Fidelity Checklist, providers are scored for low (1), moderate (2), or high (3) adherence to each essential element of treatment, and fidelity is measured by the total score.

TAU Study Arm: Following usual procedures, providers at the TAU arm PCC will refer adolescents who request mental health care or are suspected of mental illness to Psychiatric Technicians or psychologists at the primary care clinic. Trained research assistants will then inform these adolescents and their caregivers about the proposed study. If interested, research assistants

will administer the brief demographic questionnaire and the PHQ-A to determine eligibility. For eligible adolescents, For eligible adolescents, research assistants will conduct informed consent and assent procedures. Adolescents will be referred to treatment by mental health specialists at the PCC, per existing protocol. Research assistants will visit the PCC at the patients' treatment appointment times to collect data on depression symptoms and functioning. Similar to protocol for the IPT-A arm, data will be collected using the PHQ-A at treatment initiation, 6 weeks after treatment initiation, 12 weeks after treatment initiation, and 24 weeks after treatment initiation. While the treatment timeline in TAU will not necessarily be aligned with IPT-A (e.g. 12 weeks may not be the end of treatment that is provided), we will use these timepoints for both IPT-A and TAU adolescents to measure symptom improvement over time consistently across study arms. The Project Coordinator will call adolescents who do not enter or who discontinue treatment to arrange data collection at these time points. For adolescents who do not enter treatment, the first scheduled session will be considered the "treatment initiation" timepoint.

Post Treatment Data Collection: After the final treatment session (either full course of treatment or after the adolescent discontinues treatment), research assistants will conduct semi-structured exit interviews with participating adolescents and their caregivers (IPT-A arm only), which will be digitally audio-recorded, to collect feedback on acceptability and appropriateness of the depression care they received. Research assistants will also conduct exit interviews, which will be digitally-audio recorded, with PCC providers (IPT-A arm only) after the completion of the pilot trial period to collect feedback on acceptability and appropriateness of depression care they provided. Data on treatment penetration (number adolescents entering treatment/ number referred), feasibility (retention in treatment, measured as number of treatment sessions completed/number of planned treatment sessions), and sustainability (penetration and retention in the 6 months following trial end) will be collected by research assistants from clinic records (both study arms).

STATISTICAL PROCEDURES

Quantitative analysis: Power was calculated conservatively based on participation of 90 adolescents, anticipating possible loss-to-follow up of ~10% as seen in similar trials (Bolton, Bass et al. 2007, Murray, Skavenski et al. 2015). Assuming an intra-PCC correlation coefficient of 0.02-

0.10,(Hemming, Girling et al. 2011) we will have 80% power to detect a moderate 0.6 to large >1.0 effect size of continuous outcomes using a two-sided z-test with an alpha level of 0.05. All analyses between arms will be based on intention to treat. Symptom change between baseline and treatment midpoint, treatment end, and 3- month follow-up will be compared in the IPT-A versus TAU study arms through mixedmodels linear regression analysis, treating PCC as a random effect and baseline symptoms and treatment arm as fixed effects. Subsequently, patient age and gender will be introduced into the model as independent fixed effects to adjust for their potential effect on symptom change. Similar analyses will be used to compare penetration, retention, and sustainability across arms. Within each arm, I will conduct exploratory analyses of the effect of adolescent age and gender on symptom change as well as provider age, gender, and years working in PCCs on fidelity to treatment using linear regression.

Qualitative analysis: Patient and provider perspectives on acceptability and appropriateness of IPT-A or TAU will be evaluated using the Framework Method (Spencer and Ritchie 2002, Gale, Heath et al. 2013). All interviews will be digitally recorded, professionally transcribed, and loaded into Dedoose software for qualitative data management and analysis. We will independently read all transcripts and develop an open coding schema based on a priori and emergent themes. We will use Dedoose to code all data consistent with the Analytic Framework. To establish coding reliability, two research team members will independently code up to 10% of the transcripts. We will meet weekly during this process to review definitions and assignments of codes and to resolve differences until interrater reliability Kappa coefficient is higher than 0.7.(Landis and Koch 1977) If additional codes emerge during this process, they will be added to the codebook. Once all data are coded, they will be charted and assessed with a framework matrix.

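### The PHQ-A outcome is collected by providers within treatment sessions in the IPT-A arm and by research assistants in TAU, so on the planned route assessor type coincides with arm

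*Combined protocol and SAP*

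**What the plan says.** The section on the IPT-A (Treatment) Study Arm assigns outcome collection to providers: "As part of each Group IPT-A session, providers will collect data from adolescents on depression symptoms using the PHQ-A at treatment initiation", followed by weeks 6, 12 and 24. The Study Design section says who runs the groups: "Two providers (nurses and/or medical technicians) per clinic will be trained to facilitate group IPT-A". The natural reading is that the treating facilitators collect the outcome, although the text does not say so outright.

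The TAU Study Arm section has research assistants visit the clinic at appointment times to collect depression symptoms and functioning, using the PHQ-A at the same four time points. It explains the shared time points by the wish to measure symptom improvement in the same way in both arms.

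For participants off treatment, both arm sections say: "The Project Coordinator will call adolescents who do not enter or who discontinue treatment to arrange data collection at these time points". Neither names the person who then administers the PHQ-A.

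Under Statistical Procedures, symptom change from baseline is compared between arms by a linear mixed model with clinic as a random effect and baseline symptoms and arm as fixed effects; age and gender are added later. There is no assessor term, and no primary outcome is designated.

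**The concern.** The plan aims for uniform measurement but makes only the time points uniform. An adolescent in IPT-A reports symptoms within a therapy session, probably to the person treating them. An adolescent in TAU reports to a research assistant with no part in the treatment.

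That difference could act either way. Wishing to report improvement to one's own therapist would favour IPT-A. Fuller disclosure to a trusted provider would work against it. In either case the effect would be read as a treatment effect, or would hide one. PHQ-A change is one of the outcomes compared between arms, and the plan hypothesises better patient outcomes with IPT-A and intends the findings to inform scale-up.

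**Working it through.** **1. The two procedures side by side**

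| | IPT-A | TAU |
|---|---|---|
| Outcome assessor | Providers | Research assistants |
| Setting | Part of Group IPT-A sessions | Clinic visit at appointment times |
| Time points | Initiation, weeks 6, 12, 24 | Same |
| Non-entrants, discontinuers | Assessor not named | Assessor not named |
| Screening or eligibility PHQ-A | Providers | Research assistants |

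Week 24 is unclear in both arms. IPT-A ends at week 12, so collection within a session cannot apply literally at week 24, although providers are still named. TAU collection is tied to appointments that need not exist at week 24.

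**2. Can the model separate the two effects?** No, on the planned route. Assessor type does not vary within a clinic and equals arm. Neither the clinic random effect nor baseline, age or gender carries separate information about it.

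**3. The plan's own figure.** The power statement uses 90 adolescents, ICC 0.02-0.10, 80% power and a two-sided 5% z-test, and gives detectable effects of 0.6 to above 1.0. Assume four equal clinics, so m = 90/4 = 22.5.

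- Design effect = 1 + (m - 1) × ICC = 1 + 21.5 × 0.02 = 1.43, or 1 + 21.5 × 0.10 = 3.15.
- SE of the standardised difference = √(4 × 1.43/90) = 0.252, or √(4 × 3.15/90) = 0.374.
- Detectable effect = (1.96 + 0.84) × SE = 0.71 or 1.05.

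The upper end agrees with the plan; the 0.6 does not reproduce. That is a separate matter and this point does not depend on it.

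**4. Illustration: an assessor shift that develops over time.** The shift b is assumed to be 0.2 to 0.4 SD towards IPT-A (1 to 2 points at an assumed SD of 5), with no true effect. The SE is not reduced for baseline adjustment.

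- z reference: P(|Z + b/SE| > 1.96).
- t reference: noncentral t with 4 - 2 = 2 df, critical value 4.303, noncentrality b/SE.

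| b | z, ICC 0.02 | z, ICC 0.10 | t, ICC 0.02 | t, ICC 0.10 |
|---|---|---|---|---|
| 0.2 | 12.5% | 8.3% | 7.9% | 6.3% |
| 0.4 | 35.5% | 18.8% | 16.0% | 10.2% |

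Both references are shown because the plan states no degrees-of-freedom method. If the SD is 4 to 6, b runs from 1/6 = 0.17 to 2/4 = 0.50. The ranges become 10-51% and 7-27% by z, and 7-22% and 6-13% by t.

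**5. Illustration: a constant offset.** Suppose one arm is shifted by d at both baseline and follow-up. Raw change cancels it. With baseline as a covariate, the arm contrast is d - slope × d = (1 - slope) × d, where slope is the within-arm regression of follow-up on baseline. Assumed values:

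- slope 0.7, d = 0.2 SD: 0.3 × 0.2 = 0.06 SD.
- slope 0.3, d = 0.4 SD: 0.7 × 0.4 = 0.28 SD.

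Against the plan's 0.6, that is 0.06/0.6 = 10% to 0.28/0.6 = 47%. Against the recomputed 0.71 it is 8-39%; against 1.05, 6-27%.

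**The case against.** The strongest reply is that the mode of administration is not stated. Screening is described as "paper-based depression screening as part of routine clinical care". If adolescents fill in the outcome form themselves, the assessor only hands it out and takes it back. That would probably shrink any effect, and it stands as a limit on size. It does not settle the mode: the word describes screening, and provider training includes role-play to "practice administration of the PHQ-A with corrective feedback and evaluations". Research assistants are also described as trained, which may limit the effect further but does not make the assessors the same.

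Second, the overlap of assessor and arm is not complete. Off-treatment participants have no named assessor in either arm, and the collecting providers are not expressly the facilitators. Hence the restriction to the planned route. If other clinic providers collected the form, assessor type would still differ by arm.

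Third, the size rests on assumption. The shift, SD and slope come from no document. The z rates treat the variance as known. If clinic variance were estimated from four clinic means and 1.96 still used, the no-shift rejection rate would already be 1 - 1.96/√(1.96² + 2) = about 19%. The 5% starting point under z is therefore an idealisation, and the t figures show a smaller inflation. The 47% combines the largest assumed offset with the lowest slope and the smallest benchmark. All this is fair, and it bears on size only.

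Fourth, this is a four-clinic pilot, and collecting data within care is a pragmatic choice. But the plan still compares symptom change between arms.

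**Conclusion.** The concern holds. The difference in assessors is explicit, and on the planned route the stated model cannot separate it from treatment; confidence in both is high. Whether it produces bias, how much and in which direction cannot be told from the documents. The calculated figures are illustrations on assumed shifts, SDs and slopes, with equal clinics and N = 90. This is an inexpensive improvement to make, not a demonstrated bias.

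**What to change.** Amend the two arm sections so that research assistants collect the outcome PHQ-A in both arms at all four time points, including week 24 and including non-entrants and discontinuers, with the same script and out of the therapist's presence. Record the assessor each time. State that the analysis baseline is this treatment-initiation PHQ-A, not the screening or eligibility one. A PHQ-A taken by a provider in session is for clinical use and is not the trial outcome. The alternative is the same sealed self-completion in both arms, if participants can self-complete, which the documents do not say.

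Apply the change only to participants whose baseline PHQ-A has not been taken. For those already enrolled, keep the assessor type constant and report results by assessor. With partial enrolment that split would follow enrolment date and be weak evidence, and if all baselines are complete the main change comes too late. The documents do not show enrolment status.

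**Cost.** No new staff role is needed. Research assistants already do this task in TAU and already work in the IPT-A clinics: "trained research assistants will introduce the study to adolescents who screen positive for depression and their caregivers", and they also conduct exit interviews and abstract clinic records. With equal arms the added load is 45 × 4 = 180 questionnaires (90 enrolled) to 50 × 4 = 200 (100 enrolled, about 10% lost), plus separate contacts and week-24 visits. Research-assistant capacity is not stated. If in-session forms continue, IPT-A adolescents complete the PHQ-A more often than TAU adolescents, a smaller asymmetry that should be reported. The change equalises assessors; it does not blind them, and it leaves the different recruitment routes (screening in IPT-A, referral in TAU) as they are.

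### The stated 80% power for an effect of 0.6 does not follow from the plan's own inputs, and the four-clinic design leaves 2 degrees of freedom that neither the power calculation nor the analysis model accounts for

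*Combined protocol and SAP*

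**What the plan says.** All of the relevant text is in the combined protocol and SAP.

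- **Sample size (Statistical Procedures, Quantitative analysis).** "Power was calculated conservatively based on participation of 90 adolescents", "anticipating possible loss-to-follow up of ~10% as seen in similar trials". The ICC is taken as 0.02 to 0.10 and alpha as 0.05. The claim is that "we will have 80% power to detect a moderate 0.6 to large >1.0 effect size of continuous outcomes using a two-sided z-test".
- **Design (Study Design).** Four primary care clinics are randomized, two to each arm.
- **Analysis (Quantitative analysis).** Symptom change is compared by linear mixed regression, "treating PCC as a random effect and baseline symptoms and treatment arm as fixed effects". No degrees-of-freedom method or reference distribution is given. The plan adds: "Similar analyses will be used to compare penetration, retention, and sustainability across arms".
- **Aim (Research Aims & Abstracts).** "We hypothesize that the IPT-A arm will have better patient and implementation and patient outcomes than TAU".

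The plan gives no baseline correlation for the power calculation and does not say whether 90 is the number before or after the expected loss.

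**The concern.** The power sentence is the only sample-size justification, and the trial states a superiority hypothesis. The sentence pairs a range of ICCs with a range of effects, so it reads as 0.6 at ICC 0.02 and just over 1.0 at ICC 0.10. If the lower figure does not follow from the inputs, readers will credit the trial with 80% power for a moderate effect that it does not have. They could then read a null result as evidence against such an effect.

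The z-test raises a second issue. Treatment is assigned to clinics, so the arm effect must be judged against variation between clinics, and four clinics say little about that variation. A normal reference treats it as known. This makes the power figure optimistic. If the same reference is used in the analysis, a nominal 5% test will reject too often when there is no effect.

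**Working it through.** **Inputs.** N = 90, ICC 0.02 to 0.10, 80% power, two-sided alpha 0.05 (Quantitative analysis); four clinics, two per arm (Study Design). Assumed here: equal clinic sizes (90/4 = 22.5), outcome SD = 1 and, to begin with, no gain from baseline adjustment.

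**Step 1: the plan's figure on its own z basis.**

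Design effect DE = 1 + (N/4 − 1) × ICC. SE of the arm difference = √(4 × DE/N). Detectable effect = (1.960 + 0.842) × SE.

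| ICC | DE | SE | Detectable effect | Plan |
|---|---|---|---|---|
| 0.02 | 1 + 21.5 × 0.02 = 1.43 | √(5.72/90) = 0.252 | 2.802 × 0.252 = 0.706 | 0.6 |
| 0.10 | 1 + 21.5 × 0.10 = 3.15 | √(12.6/90) = 0.374 | 2.802 × 0.374 = 1.048 | >1.0 |

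The upper end reproduces, which suggests that this is the type of formula used. The lower end does not. Power for 0.6 at ICC 0.02 is Φ(0.6/0.252 − 1.960) = 66%.

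**Step 2: can another reading recover 0.6?**

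- If 90 is before loss and 81 are analysed: 0.73 and 1.06.
- If 100 are analysed: 0.68 and 1.03.
- With N = 90, a detectable effect of 0.60 needs an ICC of about 0.0015, below the stated range.
- At ICC 0.02, 0.60 needs about 152 adolescents in four clinics (unadjusted).
- Suppose a baseline correlation r reduces only the within-clinic variance, so that SE = √(4 × [(1 − r²)(1 − ICC) + (N/4) × ICC]/N). The values of r below are assumptions, not plan figures.

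| r | ICC 0.02 | ICC 0.10 |
|---|---|---|
| 0.50 | 0.643 | 1.010 |
| 0.55 | 0.629 | 1.002 |
| 0.637 | 0.600 | 0.986 |

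**Step 3: the degrees of freedom the design leaves.**

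Four clinics minus two arm means leave 2 df. The two-sided 5% critical value is then 4.303 instead of 1.960, and the noncentrality needed for 80% power is 5.653 instead of 2.802.

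| Quantity (N = 90) | ICC 0.02 | ICC 0.10 |
|---|---|---|
| Detectable effect, unadjusted | 5.653 × 0.252 = 1.43 | 5.653 × 0.374 = 2.12 |
| Detectable effect, r = 0.5 (assumed) | 1.30 | 2.04 |
| Power for 1.0 SD: 2 df (z) | 56% (98%) | 33% (76%) |

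Power for 0.6 at ICC 0.02 on 2 df is 28%.

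**Step 4: type I error of the analysis.**

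Balanced four-clinic trials with no arm effect were simulated (400,000 per setting, 22 adolescents per clinic). The random-intercept model was fitted by REML with the clinic variance held at or above zero.

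| Reference for the arm effect | ICC 0.02 | ICC 0.05 | ICC 0.10 |
|---|---|---|---|
| Wald z | 7.0% | 10.3% | 13.6% |
| Wald z, r = 0.5 (assumed) | 7.7% | 11.5% | 14.7% |
| t on 2 df, clinic means | 5.0% | 5.0% | 5.0% |

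Using 2 df with the bounded REML fit overcorrects: its type I error is only about 0.03% at ICC 0.02 and 0.75% at ICC 0.10 (22.5 per clinic). The variance estimate therefore has to be specified along with the degrees of freedom.

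**The case against.** The strongest defence is that the planned model adjusts for baseline symptoms, so an unadjusted 0.71 is not the right comparator. With a within-clinic baseline correlation of 0.5 to 0.55, the detectable effects round to 0.6 and to 1.0 or just above, which fits the sentence at the one decimal it uses. An omitted input plus rounding may therefore explain the figure as well as a slip in arithmetic does. That much stands. But the correlation appears nowhere in the plan, power at exactly 0.60 would still be only 74% to 76%, and adjustment leaves the 2-df problem almost untouched (1.30 to 2.04 SD).

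Second, the z-test is named for the power calculation only. The plan does not prescribe a Wald z for the mixed model, so the inflated error rates are conditional on that choice. This is correct: the fault is an open choice, not a specified wrong one.

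Third, this is a pilot with feasibility, acceptability and qualitative aims, for which formal power matters less. That is fair, but the plan chose to state 80% power, set alpha at 0.05 and hypothesize superiority, and those statements should be right.

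Finally, the extension to penetration, retention and sustainability rests on the shared design of four clinics. The figures here are for continuous outcomes only.

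**Conclusion.** The concern holds. On the plan's stated inputs, 80% power is available for 0.71 SD at ICC 0.02, not 0.6, while the upper end is consistent with the plan. Either the lower figure is wrong or an input that decides it was left out.

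The larger fault does not depend on how that is resolved. With 2 between-clinic df, the detectable effects are about 1.4 to 2.1 SD, roughly double the z-based values. Without a stated reference distribution, 5% error control for the arm comparison is not secured.

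These figures assume equal clinic sizes; unequal sizes would lower power further. Except where a baseline correlation is shown, they also assume no gain from baseline adjustment.

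**What to change.** **1. Restate the power sentence with its assumptions.** For example: with 90 adolescents in four clinics of equal size, before any gain from baseline adjustment, and an ICC of 0.02 to 0.10, 80% power is available for about 0.71 to 1.05 SD under a large-sample z approximation and for about 1.4 to 2.1 SD with 2 between-clinic degrees of freedom. Say whether 90 is before or after the 10% loss. If a baseline correlation was assumed, give its value and source and add the adjusted figures, so that the power statement matches the planned model.

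**2. State the reference distribution.** For example: the arm effect will be referred to t with 2 between-clinic degrees of freedom, using a t-test of baseline-adjusted clinic means or a REML fit in which the clinic variance is not bounded at zero, and will be reported with its 95% confidence interval. It should not be left to a software default. Say also how the arm comparisons of penetration, retention and sustainability will allow for having only four clinics.

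**Cost.** One revised sentence and one or two new ones; no added adolescents, clinics or data. The stated detectable effect becomes less favourable. For the same standard error, intervals are 4.30/1.96 = 2.2 times as wide as under a z reference, though the plan does not say that z was intended for the analysis.
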